5.6 Prior and Concomitant Medications and/or Procedures

5.6.1 Excluded Medications and/or Procedures

The following medications and/or procedures are excluded:

- Platelet transfusion or receipt of blood products containing platelets within 7 days of the Baseline Visit; however, packed red blood cells are permitted;

- Use of anticoagulant or antiplatelet therapy (other than low dose aspirin) on Visit 4 (Procedure Day)
- Use of erythropoietin-stimulating agents within 7 days of the Baseline Visit;
- Use of moderate or strong inducers of CYP2C9 or CYP3A4/5 from 7 days prior to Baseline through the end of the dosing regimen (see Appendix C);
- Use of thrombopoietin receptor agonists (eg, eltrombopag or romiplostim);
- Use of systemic antibiotic therapy within 7 days of the Baseline Visit; however, prophylactic use of antibiotics is permitted;
- A surgery between the Baseline Visit and Visit 4 (Procedure Day); and
- Currently enrolled in another clinical study with any investigational drug or device within 30 days of the Baseline Visit; however, participation in observational studies is permitted.

5.6.2 Documentation of Concomitant Medication Use

All concomitant medications (including concurrent therapies and concurrent procedures) will be documented as indicated in Appendix A. Dose, indication for administration, and dates of medication administration will also be captured in source documents and on the appropriate eCRF.

6 STUDY PROCEDURES

A schedule of procedures in tabular format is provided in Table 1 in Appendix A.

Local laboratories will be used to determine eligibility; however, for study analysis and reporting purposes, only values determined at a central laboratory will be used with the exception of platelet count. Local laboratories may be used if immediate results are clinically needed.

Two platelet counts collected on different days must be used to calculate the mean baseline platelet count to determine eligibility as described in Inclusion Criterion #2. If a platelet count obtained per standard of care within 14 days of Baseline (Visit 2) is not available, a platelet count must be obtained at Screening (Visit 1) and then repeated at Baseline (Visit 2) to confirm eligibility. If an eligible platelet count obtained per standard of care is available from this time period, Visit 1 is not required and all Screening and Baseline procedures can be performed at Visit 2.

6.1 Informed Consent

Prior to conducting any study-related activities, written informed consent must be signed and dated by the subject (or legally authorized representative). See Section 11.3 for additional information on informed consent.

6.2 Screening

6.2.1 Visit 1 – Screening Visit (optional)

If an eligible platelet count obtained per standard of care within 14 days of the Baseline visit is available, this visit is not required and study procedures may commence as described for Visit 2. The following procedures will be performed at the Screening Visit at Visit 1 (Day -14 to Day -1):

- Obtain informed consent prior to screening procedures;
- Obtain demographics and medical history (including etiology of thrombocytopenia);
- Collect blood samples for the following assessments:
 - Platelet count (local and central laboratories),
- Contact IRT to register the subject in the study.

6.2.2 Visit 2 - Baseline Visit

The following procedures will be performed prior to study drug administration at the Baseline Visit at Visit 2 (Day 1):

- Obtain informed consent prior to screening procedures, if Visit 1 not performed;
- Conduct eligibility assessment based on inclusion/exclusion criteria;
- Obtain demographics and medical history (including etiology of thrombocytopenia), if Visit 1 not performed;
- Collect procedure-related information;
- Record concomitant medications;
- Assess adverse events;

- Perform physical examination;
- Record vital signs (includes weight, body temperature, blood pressure, and pulse rate);
- Record an eligible platelet count collected within the previous 14 days, if available; Collect blood samples for the following assessments (-1 Day permitted):
 - Hematology (local and central laboratories),
 - Platelet count (local and central laboratories);
 - Coagulation (local and central laboratories);
 - Serum chemistry (central laboratory only); and
 - Pregnancy test for female subjects of childbearing potential only (serum or urine);
- Contact IRT;
- Dispense study drug; and
- Administer or self-dose study drug.

6.3 Treatment Period

Subjects will receive 60 mg oral avatrombopag once daily for 5 days. For study site visits during the Treatment Period, study drug may be administered at the site or the subject may self-dose. Subjects will self-dose at all other times and be instructed to take study drug with food. The Investigator or designee will provide subjects with sufficient study drug to complete the 5-day regimen.

6.3.1 Visit 3

The following procedures will be performed at Visit 3 (Day 5 [-2 days]):

- Record concomitant medications,
- Assess adverse events,
- Collect blood samples for the following assessments:
 - Hematology (central laboratory only),
 - Platelet count (local and central laboratories), and
 - Coagulation (central laboratory only),
- Assess whether subject required any rescue procedure for bleeding,
- If any bleeding, perform ISTH non-surgical bleeding assessment (see Appendix D),
- Contact IRT, and
- Administer or self-dose study drug.

6.4 Visit 4 - Procedure Day

The following procedures will be performed pre-operatively on Procedure Day at Visit 4 (Day 10 [+3 days]):

- Record vital signs (includes weight, body temperature, blood pressure, and pulse rate);
- Collect blood samples for the following assessments:
 - Hematology (central laboratory only),
 - Platelet count (local and central laboratories),
 - Coagulation (central laboratory only), and
 - Serum chemistry (central laboratory only);
- Record whether subject required a platelet transfusion;
- If any bleeding, perform ISTH non-surgical bleeding assessment (see Appendix D);
- Contact IRT; and
- Collect study drug package and any unused study drug.

The following procedures will be performed post-operatively on Procedure Day at Visit 4 (Day 10 [+3 days]):

- Record concomitant medications,
- Record adverse events,
- Record whether subject required any rescue procedure for bleeding, and
- If any bleeding, perform ISTH surgical bleeding assessment (see Appendix D).

6.5 Follow-Up Period

6.5.1 Visit 5

The following procedures will be performed at Visit 5 (7 days post-procedure [+3 days]):

- Record concomitant medications;
- Assess adverse events;
- Perform physical examination;
- Record vital signs (includes weight, body temperature, blood pressure, and pulse rate);
- Collect blood samples for the following assessments:
 - Hematology (central laboratory only),
 - Platelet count (local and central laboratories),
 - Coagulation (central laboratory only), and
 - Serum chemistry (central laboratory only);
- Assess whether subject required a platelet transfusion;

- Assess whether subject required any rescue procedure for bleeding;
- If any bleeding, perform ISTH surgical and non-surgical bleeding assessment (see Appendix D); and
- Contact IRT.

6.5.2 Visit 6

The following procedures will be performed at Visit 6 (Day 35 [± 3 days]):

- Record concomitant medications;
- Assess adverse events;
- Perform physical examination;
- Record vital signs (includes weight, body temperature, blood pressure, and pulse rate);
- Collect blood samples for the following assessments:
 - Hematology (central laboratory only),
 - Platelet count (local and central laboratories),
 - Coagulation (central laboratory only), and
 - Serum chemistry (central laboratory only);
- Perform pregnancy test for female subjects of childbearing potential only (serum or urine);
- Assess whether subject required a platelet transfusion;
- Assess whether subject required any rescue procedure for bleeding;
- If any bleeding, perform ISTH surgical and non-surgical bleeding assessment (see Appendix D); and
- Contact IRT.

6.6 Early Termination Visit and Withdrawal Procedures

For subjects who are withdrawn from the study prior to completion, all Visit 6 procedures will be performed at an Early Termination Visit. These procedures include the following:

- Record concomitant medications;
- Assess adverse events;
- Perform physical examination;
- Record vital signs (includes weight, body temperature, blood pressure, and pulse rate);
- Collect blood samples for the following assessments:
 - Hematology (central laboratory only),
 - Platelet count (local and central laboratories),

- Coagulation (central laboratory only), and
- Serum chemistry (central laboratory only);
- Perform pregnancy test for female subjects of childbearing potential only (serum or urine);
- Assess whether subject required a platelet transfusion;
- Assess whether subject required any rescue procedure for bleeding;
- If any bleeding, perform ISTH surgical and/or non-surgical bleeding assessment (see Appendix D); and

Note: For an Early Termination Visit where a subject withdraws from the study prior to surgery on Procedure Day, the non-surgical ISTH bleeding definitions will be used. If a subject withdraws after surgery on Procedure Day, both the non-surgical and surgical ISTH bleeding definitions will be used.

- Contact IRT.

7 EFFICACY ASSESSMENTS

The primary efficacy endpoint is the proportion of subjects achieving a platelet count of $\geq 100 \times 10^9/L$ on Procedure Day, when measured prior to a platelet transfusion (if any).

The secondary efficacy endpoints include the following:

- Change in platelet count from baseline to Procedure Day,
- Proportion of subjects without platelet transfusion and any other treatment for bleeding after the Baseline Visit and up to 7 days following Procedure Day,
- Proportion of subjects without platelet transfusion after the Baseline Visit and up to 7 days following Procedure Day, and
- Proportion of subjects without bleeding after the Baseline Visit and up to 7 days following Procedure Day.

Blood samples to assess platelet count will be collected as indicated in Appendix A. Local laboratories will be used to determine eligibility; however, for study analysis and reporting purposes, only values determined at a central laboratory will be used with the exception of platelet count. Local laboratories may be used if immediate results are clinically needed.

Whether a subject requires a platelet transfusion will be determined by the Investigator or treating physician. Transfusion may be deemed necessary if the platelet count is below the target value of $\geq 100 \times 10^9/L$ or at the discretion of the Investigator or treating physician.

Bleeding will be evaluated by the Investigator using the non-surgical and surgical ISTH bleeding definitions described in Appendix D. The non-surgical ISTH bleeding definitions (Table 3) will be used when evaluating subjects prior to surgery on Procedure Day, and the surgical ISTH bleeding definitions (Table 4) will be used when evaluating subjects after surgery on Procedure Day. Both the non-surgical and surgical ISTH bleeding definitions will be used to evaluate subjects during the Follow-up Period. For an Early Termination Visit where a subject withdraws from the study prior to surgery on Procedure Day, the non-surgical ISTH bleeding definitions will be used. If a subject withdraws after surgery on Procedure Day, both the non-surgical and surgical ISTH bleeding definitions will be used.

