It is estimated from pharmacokinetic/pharmacodynamic modeling that the proportion of subjects treated with avatrombopag expected to achieve a platelet count of $\geq 100 \times 10^9/L$ on Procedure Day, when measured prior to platelet transfusion (if any), is approximately 85%. Assuming the true response rate is 0.8 and the desired lower boundary of the 2-sided 95% CI is at least 0.65, 60 enrolled subjects will provide greater than 90% power. If the decision is made to increase the dose of study drug at one of the interim reviews of the data based on the pre-defined boundaries, up to an additional 30 subjects may be enrolled in the study for a maximum sample size of 90 subjects.

SITES: Approximately 30 sites in the United States

SPONSOR:

Dova Pharmaceuticals
[name]
[name]
United States
[contact]
[contact]

TABLE OF CONTENTS

Signature Page	2
Investigator Agreement.....	3
Synopsis	4
Table of Contents.....	8
List of Tables	12
List of Abbreviations and Definition of Terms.....	13
1 Introduction and Background Information	14
1.1 Thrombocytopenia	14
1.2 Avatrombopag.....	14
1.3 Nonclinical Studies	15
1.4 Clinical Studies	15
1.4.1 Phase 1 Studies.....	15
1.4.2 Phase 2 Studies.....	16
1.4.3 Phase 3 Studies.....	17
1.5 Rationale.....	18
1.6 Risk/Benefit.....	19
2 Study Objectives	20
2.1 Primary Objective	20
2.2 Secondary Objectives.....	20
3 Study Description.....	21
3.1 Summary of Study Design	21
3.2 Study Indication	21
4 Selection and Withdrawal of Subjects	22
4.1 Inclusion Criteria.....	22
4.2 Exclusion Criteria.....	22
4.3 Withdrawal Criteria.....	24
4.3.1 Subjects with Study Drug Interruption or Discontinuation.....	24
5 Study Treatments	25
5.1 Treatment Groups.....	25
5.2 Rationale for Dosing	25

5.3	Randomization and Blinding.....	25
5.4	Breaking the Blind	25
5.5	Drug Supplies.....	26
5.5.1	Formulation and Packaging.....	26
5.5.2	Study Drug Preparation and Dispensing.....	26
5.5.3	Study Drug Administration.....	26
5.5.4	Treatment Compliance	26
5.5.5	Storage and Accountability.....	26
5.6	Prior and Concomitant Medications and/or Procedures.....	26
5.6.1	Excluded Medications and/or Procedures.....	26
5.6.2	Documentation of Concomitant Medication Use.....	27
6	Study Procedures	28
6.1	Informed Consent.....	28
6.2	Screening.....	28
6.2.1	Visit 1 – Screening Visit (optional).....	28
6.2.2	Visit 2 - Baseline Visit	28
6.3	Treatment Period.....	29
6.3.1	Visit 3	29
6.4	Visit 4 - Procedure Day.....	30
6.5	Follow-Up Period.....	30

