9.2.1.2 Secondary efficacy analysis

The following secondary efficacy endpoints will be summarized and analyzed in the same manner as the primary efficacy endpoint:

- Proportion of subjects without platelet transfusion and any other treatment for bleeding after the Baseline Visit and up to 7 days following Procedure Day,
- Proportion of subjects without platelet transfusion after the Baseline Visit and up to 7 days following Procedure Day, and
- Proportion of subjects without bleeding after the Baseline Visit and up to 7 days following Procedure Day.

Change in platelet count from baseline to Procedure Day for avatrombopag will be calculated for each subject and summarized descriptively. The mean (95% CI) and median (range) will be provided.

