 6. For female subjects of childbearing potential only. A serum or urine pregnancy test will be performed at the Baseline Visit prior to study drug administration.
 7. Either a serum or urine pregnancy test may be used.
 8. Subjects will receive 60 mg oral avatrombopag once daily for 5 days beginning on Day 1. For study site visits during the Treatment Period, study drug may be administered at the site or the subject may self-dose. Subjects will self-dose at all other times and be instructed to take study drug with food. The Investigator or designee will provide subjects with sufficient study drug to complete the 5-day regimen.
 9. Bleeding will be evaluated, if present, by the Investigator using the non-surgical and surgical ISTH bleeding definitions described in Appendix D. The non-surgical ISTH bleeding definitions (Table 3) will be used when evaluating subjects prior to surgery on Procedure Day, and the surgical ISTH bleeding definitions (Table 4) will be used when evaluating subjects after surgery on Procedure Day. Both the non-surgical and surgical ISTH bleeding definitions will be used to evaluate subjects during the Follow-up Period. For an Early Termination Visit where a subject withdraws from the study prior to surgery on Procedure Day, the non-surgical ISTH bleeding definitions will be used. If a subject withdraws after surgery on Procedure Day, both the non-surgical and surgical ISTH bleeding definitions will be used.
 10. Document etiology of thrombocytopenia.
 11. If Visit 1 not performed
- ET = Early Termination; IRT = Interactive Response Technology; ISTH = International Society on Thrombosis and Haemostasis.

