APPENDIX D: INTERNATIONAL SOCIETY ON THROMBOSIS AND HAEMOSTASIS BLEEDING DEFINITIONS

Table 3 Non-Surgical International Society on Thrombosis and Haemostasis Bleeding Definition

Major bleeding	
Defined as overt bleeding with 1 or more of the following:
 
 • Associated with a fall in hemoglobin level of 20 g/L (1.24 mmol/L) or more; • Leads to a transfusion of 2 or more units of packed red blood cells or whole blood; • Occurs in a critical site: intracranial, intraspinal, intraocular, pericardial, intra-articular, intramuscular with compartment syndrome, retroperitoneal; and/or • Contributes to death.
Non-major clinically relevant bleeding	
Defined as overt bleeding not meeting the criteria for major bleeding, but associated with medical intervention, unscheduled contact with a physician (visit or telephone call), (temporary) cessation of study treatment, or associated with any other discomfort, such as pain or impairment of daily activities. Examples of such bleeding include:
 
 • Any bleeding compromising hemodynamics; • Any bleeding leading to hospitalization; • Epistaxis if it lasts for >5 minutes, if it is repetitive (ie, ≥ 2 episodes of true bleeding, [ie, not spots on a handkerchief] within 24 hours), or if it leads to an intervention (packing, electrocoagulation, etc); • Gingival bleeding if it occurs spontaneously (ie, unrelated to tooth brushing or eating) or lasts >5 minutes; • Hematuria if it is macroscopic and either spontaneous or lasts >24 hours after instrumentation (eg, catheter placement or surgery) of the urogenital tract; • Macroscopic gastrointestinal hemorrhage (at least 1 episode of melena/hematemesis, if clinically apparent, and hemocult positive rectal blood loss, if more than a few spots on toilet paper); • Hemoptysis, if more than a few speckles in the sputum and not occurring within the context of a pulmonary embolism; • Intramuscular hematoma; • Subcutaneous (skin) hematoma if the size is >25 cm² or >100 cm² if provoked; and/or • Any other bleeding type that is considered to have clinical consequences for a subject.
Minor bleeding	
Defined as all other overt bleeding episodes not meeting the criteria for major or clinically relevant non-major bleeding.

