
Sources: Schulman S, Angeras D, Bergqvist B, et al. Definition of major bleeding in clinical investigations of antihemostatic medicinal products in surgical patients. J Thromb Haemost. 2010;8:202-204 and Tangelder M, Nwachuku C, Jaff M, et al. A review of antithrombotic therapy and the rationale and design of the randomized edoxaban in patients with peripheral artery disease (ePAD) trial adding edoxaban or clopidogrel to aspirin after femoropopliteal endovascular intervention. J Endovasc Ther. 2015; 22(2)261-268.
	

Table 4 Surgical International Society on Thrombosis and Haemostasis Bleeding Definition

Major bleeding	
 • Fatal bleeding; • Bleeding that is symptomatic and occurs in a critical area or organ, such as intracranial, intraspinal, intraocular, retroperitoneal, pericardial, in a non-operated joint, or intramuscular with compartment syndrome, assessed in consultation with the surgeon; • Extrasurgical site bleeding causing a fall in hemoglobin level of 20 g/L (1.24 mmol/L) or more, or leading to transfusion of 2 or more units of whole blood or red cells, with temporal association within 24 to 48 hours to the bleeding; • Surgical site bleeding that requires a second intervention – open, arthroscopic, endovascular – or a hemarthrosis of sufficient size as to interfere with rehabilitation by delaying mobilization or delayed wound healing, resulting in prolonged hospitalization or a deep wound infection; and • Surgical site bleeding that is unexpected and prolonged and/or sufficiently large to cause hemodynamic instability, as assessed by the surgeon. There should be an associate fall in hemoglobin level of at least 20 g/L (1.24 mmol/L), or transfusion, indicated by the bleeding, of at least 2 units of whole blood or red cells, with temporal association within 24 hours to the bleeding.
Minor bleeding	Defined as all other overt bleeding episodes not meeting the criteria for major bleeding.

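### Does the secondary endpoint of freedom from bleeding need a grade threshold and a rule for expected operative bleeding?

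*Protocol*

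**What the plan says.** Section 7 lists as a secondary endpoint the "Proportion of subjects without bleeding after the Baseline Visit and up to 7 days following Procedure Day". The Synopsis and Section 9.2.1.2 use the same wording. None of these places names a grade. On the analysis, Section 9.2.1.2 says "The following secondary efficacy endpoints will be summarized and analyzed in the same manner as the primary efficacy endpoint", which means a binomial proportion with a 95% confidence interval.

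Section 7 has the Investigator evaluate bleeding with the two ISTH tables in Appendix D. The non-surgical table (Table 3) applies before surgery on Procedure Day and the surgical table (Table 4) after it. For later visits, "Both the non-surgical and surgical ISTH bleeding definitions will be used to evaluate subjects during the Follow-up Period".

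The assessment is done only when there is bleeding. Among the post-operative procedures, Section 6.4 has "If any bleeding, perform ISTH surgical bleeding assessment (see Appendix D". Footnote 9 of the Schedule of Procedures says "Bleeding will be evaluated, if present, by the Investigator using the non-surgical and surgical ISTH bleeding definitions described in Appendix D".

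Table 3 has three grades. The middle one begins "Defined as overt bleeding not meeting the criteria for major bleeding, but associated with medical intervention, unscheduled contact with a physician". Table 4 has two grades, major and minor, and the minor grade is "Defined as all other overt bleeding episodes not meeting the criteria for major bleeding".

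**The concern.** Read literally, a single overt bleed of any grade makes a subject a failure, and the window contains an operation chosen for its critical site or its bleeding risk. The minor grade in each table is a catch-all. Expectedness appears only inside one criterion for major surgical-site bleeding, so it does not keep ordinary operative blood loss out of the minor grade. One investigator could enter such loss as minor bleeding and another could enter nothing, and both would be within the text. The Synopsis plans "Approximately 30 sites in the United States".

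The effect on bleeding is one of the three secondary objectives in Section 2.2. In a single-arm study there is no control group in which recording habits would cancel. If minor operative bleeding made up most of the failures, the proportion would say little about bleeding that matters clinically. An analysis plan can choose grades afterwards, but it cannot recover bleeds that were never entered.

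**Working it through.** The protocol states no bleeding rate, power or target for this endpoint, so there is no planned figure to reproduce. The check has two parts.

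**1. What the text leaves open**

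| Question | Where the protocol answers |
|---|---|
| What counts as bleeding? | Section 7 refers to the ISTH definitions in Appendix D |
| Can any overt bleed fall outside the grades? | No. Both tables end in a minor grade that takes all remaining overt bleeding |
| Which grades make a subject a failure? | No restriction is stated, so any grade does |
| When is the surgical table applied? | After surgery on Procedure Day (Sections 6.4 and 7, Schedule footnote 2) and in follow-up |
| Is expected operative blood loss an episode? | Not stated |

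Only the last row is a true gap.

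**2. Sensitivity of the proportion to recording**

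Inputs from the protocol: n = 60 planned, n = 90 at most (Section 9.2.4), about 30 sites (Synopsis). Assumptions: 70%, 80% or 90% of subjects would be bleed-free if minor operative bleeding were not entered.

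One subject moves the proportion by 1/60 = 1.7 percentage points, or 1/90 = 1.1 points. For x bleed-free subjects out of n, take the exact (Clopper-Pearson) 95% lower limit L and find the smallest k with (x − k)/n < L.

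| n | x | L | k | (x − k)/n | k/n |
|---|---|---|---|---|---|
| 60 | 42 | 0.568 | 8 | 34/60 = 0.567 | 13% |
| 60 | 48 | 0.677 | 8 | 40/60 = 0.667 | 13% |
| 60 | 54 | 0.795 | 7 | 47/60 = 0.783 | 12% |
| 90 | 63 | 0.594 | 10 | 53/90 = 0.589 | 11% |
| 90 | 72 | 0.7025 | 9 | 63/90 = 0.700 | 10% |
| 90 | 81 | 0.819 | 8 | 73/90 = 0.811 | 9% |

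With even enrolment (assumed), 60/30 = 2 subjects per site. Eight subjects would then be everyone at 8/2 = 4 sites, provided that each had only this kind of bleeding.

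A second illustration asks how far minor bleeds could dominate. Let a be the share of subjects with a more serious bleed, and m the share of the rest with only a recorded minor or operative bleed. Both are assumed. The bleed-free proportion is (1 − a)(1 − m), and the minor-only share of failures is (1 − a)m / [1 − (1 − a)(1 − m)].

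- a = 0.05, m = 0.10: bleed-free 0.95 × 0.90 = 0.855; minor-only share 0.095/0.145 = 66%.
- a = 0.05, m = 0.50: bleed-free 0.95 × 0.50 = 0.475; minor-only share 0.475/0.525 = 90%.
- a = 0.10, m = 0.10: bleed-free 0.90 × 0.90 = 0.81; minor-only share 0.09/0.19 = 47%.

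These figures show that the proportion could move. They do not show that it will. The first table would look the same for any binary endpoint with these rates and sample sizes, and nothing in the protocol informs m.

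**The case for a change.** The strongest case for a change is that recording is decided at the bedside, under Section 6.4 and the Schedule footnotes. That is protocol text, and no later plan can make it uniform. Treated bleeding already has its own secondary endpoint, so this one ought to isolate clinically relevant bleeding. A remedy would also be cheap: count major bleeds, add the clinically relevant non-major grade where Table 3 applies, use the more severe grade in follow-up, and tell sites that expected operative loss is not an episode.

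The recording point stands in part, since the protocol text gives no rule. It does not follow that sites have none. Section 11.4 has the sponsor or its designee go through the eCRFs and their completion procedures with each site before enrolment, and such an instruction normally sits there. Two features also narrow the gap without closing it: the surgical assessment is made post-operatively, and Table 4 grades overt bleeding episodes rather than blood lost during the operation.

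The grade argument does not stand. The objective concerns bleeding, not clinically relevant bleeding. An any-bleeding endpoint complements the treated-bleeding endpoint because it also captures bleeds that needed no treatment. The choice of grades for further summaries, and the handling of two tables in follow-up, are derivations that an analysis plan can settle from the recorded grades.

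The remedy brings problems of its own:

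- Table 4 has no intermediate grade, so the least sensitive definition would apply right after surgery. The same wound haematoma could be no event on Procedure Day and a failure the next day.
- Taking the more severe grade lets Table 3 override Table 4. Table 3 calls an overt bleed major on a haemoglobin fall of 20 g/L, or on transfusion of 2 units, alone. Table 4 asks more of surgical-site bleeding.
- Expected operative blood loss would still be left to each site's judgement.

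**Conclusion.** No change to the plan follows. The endpoint is broad but defined, and it agrees with its objective; a grade threshold would be a preference with drawbacks of its own. What remains is one unwritten recording instruction, which eCRF completion guidance can supply, with bleeding reported by ISTH grade and by table beside the overall proportion.

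The size of any effect is unknown. Under assumed bleed-free rates of 70% to 90%, it takes 7 or 8 of 60 subjects, or 8 to 10 of 90, classified differently to move the estimate below its own exact 95% limit. This is a secondary endpoint with no stated target or power in an uncontrolled study. Even perfectly graded, the proportion could not by itself attribute bleeding outcomes to the drug. The primary endpoint rests on platelet counts and is untouched.
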